12.2 Serious Adverse Events

Planned Serious TEAE summary tables include:

- Incidence of Serious Treatment-Emergent Adverse Events by MedDRA System Organ Class and Preferred Term (Safety Population)
- Incidence of Serious Treatment-Emergent Adverse Events Judged Possibly, Probably or Definitely Related to the Study Drug Regimen by MedDRA System Organ Class and Preferred Term (Safety Population)
- Treatment-Emergent Adverse Events in the Standardized MedDRA Query for Tumor Lysis Syndrome Judged Possibly, Probably or Definitely Related to the Study Drug Regimen by MedDRA Preferred Term (Safety Population)

12.3 Clinical Laboratory Tests

Safety laboratory assessments will be presented in patient listings.

12.4 Vital Signs

Vital signs data will be presented in patient listings.

12.5 12-Lead Electrocardiogram (ECG)

ECG data will be presented in patient listings.

12.6 ECOG Performance Status

ECOG assessments will be presented in patient listings.

12.7 Physical Examination and Pregnancy Test

The physical examination data and pregnancy test results will be presented in patient listings.

13. PHARMACOKINETIC (PK) ANALYSIS

Not applicable.

14. PHARMACODYNAMIC (PD) ANALYSIS

Pharmacodynamic endpoints include:

- BH3 profiling, including determination of MCL-1 dependence, at Baseline and End of Treatment using bone marrow.
- Minimal residual disease (MRD) to be determined by central CLIA accredited laboratory evaluation of bone marrow samples collected at baseline and at time of response assessments using standardized techniques (i.e., MPFC and molecular testing including NGS).
- Peripheral blood and bone marrow samples will be collected at protocol- specific time points to evaluate other potential biomarkers including but not limited to MCL-1 dependence. These assessments may be explored in the context of AML or related conditions or drugs of similar class.

Any PD data analysis will be performed by SDPO R&D group and/or sponsor PD consultant.

15. COMMITMENT TO GOOD STATISTICAL PRACTICE

15.1 Definition of Good Statistical Practice

International Conference on Harmonization (ICH) Guidance on Statistical Principles for Clinical Trials (ICH E9) implicitly defines good statistical practice. Good statistical practice includes both appropriate statistical designs to minimize bias and to maximize precision of analysis plus operational excellence to assure credibility of results. The scientific design associated with any clinical trial is found in the protocol and in a more detailed pre-specified statistical analysis plan such as this one.

Due to the early termination of this study and low sample size, efficacy and safety endpoints will not be analyzed via inferential statistical methods. Descriptive statistics will be presented in the summary tables as described in this SAP, and full patient listings will be provided to enable a synoptic clinical study report to be written for this study.

15.2 Data Management and Use of CDISC Standards

Data standards for clinical development of drugs have been defined and are maturing under various initiatives through the Clinical Data Interchange Standards Consortium (CDISC).

SDPO used third party vendors for clinical data collection and data analysis. Clinical data will be managed by IQVIA (US based CRO), and will be captured in electronic case report form (eCRF) by the InForm EDC platform. The “raw” data contained in the eCRF clinical database will then be converted into Study Data Tabulation Model (SDTM) datasets per CDISC standards. The SDTM datasets will be utilized to create Analysis Data Model (ADaM) datasets. These CDISC data conversions will be conducted by Vantage Data Designs. These CDISC data conversions and data analysis will be conducted by Vantage Data Designs.

Other applicable standards include regulatory guidance's from the Food and Drug Administration (FDA), ICH Guidance on the Structure and Content of Clinical Study Reports (ICH E3), and ICH Guidance for Good Clinical Practice (ICH E6).

15.3 Testing/Validation Plan and Software System

Statistical Analysis Software (SAS) version 9.4 or later will be used to analyze the data, create summary tables, patient data listings, and graphical representation of the data. All SAS computer programs will be validated using industry standard validation procedures including independent quality control programming.

16. STATISTICAL ANALYSIS CHANGES FROM THE PROTOCOL

The analyses described are based on the final clinical study protocol TPI-ALV-202 Amendment Version 2.0 dated August 11, 2020. This SAP supersedes the statistical considerations identified in the protocol.

18. SCHEDULE OF ASSESSMENTS

Arm 1 (ALDAC)

TESTS/PROCEDURES	SCREENING												ALL TREATMENT CYCLES (CYCLE = 28 DAYS)												
	-14 days	-72 hours	D1	D2	D3	D4	D5	D6	D7	D8	D9	D10	D11	D12	D15	D22	D28	EOT	FU						
Visit window																									
Obtain ICF	X																								
Medical history	X																								
Full PE	X																								
Abbreviated PE																									
BSA																									
Weight (kg)	X																								
Height (cm)	X																								
ECOG	X																								
Vital signs	X																								
Bone marrow & peripheral blood	X																								
Cytogenetic profiling	X																								
12-lead ECG	X																								
Pregnancy test	X																								
Hematology	X																								
Full chemistry panel	X																								
Pre-infusion TLS labs																									
Post-infusion TLS labs																									
Coagulation																									
Urinalysis	X																								
Blood transfusions																									
Lumbar puncture for CNS disease	X*																								
Review Inc/Exc Criteria	X																								
Daily oral allopurinol																									

Recorded from 56 days prior to first study treatment dose, through 56 days after last dose of study treatment

Lumbar puncture for CNS disease	X*																								
Review Inc/Exc Criteria	X																								

Mandatory from 72 hours prior to D1 up to C1D28. As clinically indicated for subsequent cycles.

TESTS/PROCEDURES	SCREENING												ALL TREATMENT CYCLES (CYCLE = 28 DAYS)												
	For C1, mandatory			As indicated based on TLS symptoms												C2+***									
IV hydration pre & post infusion			X C2+***																						
Oral phosphate binder																									
Visit window			±3d C2+																						
Assess patient's hydration level																									
Prophylactic antibiotics, antifungals per site SOC																									
Antiviral per site SOC																									
Alvocidib infusion			X																						
LDAC injection				X																					
Provide / review patient diary			X	X	X	X	X	X	X	X	X	X	X	X	X	X	X	X	X	X	X	X	X	X	
Con meds																									
Assessment of AEs																									
Phone call to patient																									

a Dose is only adjusted at the beginning of each cycle after Cycle 1 if there has been a > 10% change in weight compared to the weight used to calculate the current dose.

b Required at C1 and then every even cycle thereafter (i.e. C2, C4, etc).

c Bone marrow and peripheral blood are not collected if collected in the previous 30 days.

d Year 1: Phone calls monthly (±5 days) beginning the month after the patient completes the end-of-study assessments to 12 months after End of Treatment visit regardless of how many cycles a patient receives (Year 1=Day of First Treatment plus 12 months).
Year 2: Phone calls every other month (±5 days) during Year 2 (Months 14 to 24 after End of Treatment visit).

* as clinically indicated

** only required if last pregnancy test was >72 hrs from C1D1 visit

*** optional for subsequent cycles for patients who have achieved a CR

Arm 2 (ALV)

TESTS/PROCEDURES	SCREENING				ALL TREATMENT CYCLES (CYCLE = 28 DAYS)								FU
	-14 days	-72 hours	D1	D2	D3	D4	D8	D15	D22	D28	EOT		
Visit window								±1d	±2d	±3d			±5d
Obtain ICF	X												
Medical history	X												
Full PE	X		X C2+										
Abbreviated PE			X C1					X	X C1		X		
BSA		X											
Weight (kg)	X			X a									X
Height (cm)	X												X
ECOG	X		X					X	X C1				X
Vital signs	X		X					X	X	X			X
Bone marrow & peripheral blood	X												
Cytogenetic profiling	X												
12-lead ECG	X												X*
Pregnancy test	X	X		X (**C1)									
Hematology	X	X	X C2					X	X	X			X
Full chemistry panel	X	X	X C2+					X	X	X			X
Pre-infusion TLS labs			X Only C1										
Post-infusion TLS labs			X Only C1	X Only C1	X Only C1	X Only C1	X Only C1	X Only C1	X Only C1	X			
Coagulation			X C2+*					X*	X*	X*			X*
Urinalysis		X											X
Blood transfusions													
Lumbar puncture for CNS disease		X*											
Review Inc/Exc Criteria		X											
Daily oral allopurinol													
IV hydration pre & post infusion			X C2+**						X C2+***	X C2+***			
Oral phosphate binder													
Assess patient's hydration level													

Mandatory from 72 hours prior to D1 up to C1D28. As clinically indicated for subsequent cycles.
For C1, mandatory
To be closely monitored throughout study treatment and replace excessive fluid losses unless not clinically indicated

As indicated based on TLS symptoms

TESTS/PROCEDURES	SCREENING							ALL TREATMENT CYCLES (CYCLE = 28 DAYS)							FU	
	-14 days	-72 hours	D1	D2	D3	D4	D8	D15	D22	D28	EOT	±3d	±1d	±2d	±3d	
Visit window		±3d C2+														
Antiviral per site SOC																
Alvocidib infusion		X														
Provide / review patient diary	X	X	X	X	X	X	X	X	X	X	X	X	X	X	X	
Con meds																
Assessment of AEs																
Phone call to patient																X d

e Dose is only adjusted at the beginning of each cycle after Cycle 1 if there has been a > 10% change in weight compared to the weight used to calculate the current dose.

f Required at C1 and then every even cycle thereafter (i.e. C2, C4, etc).

g Bone marrow and peripheral blood are not collected if collected in the previous 30 days

h Year 1: Phone calls monthly (± 5 days) beginning the month after the patient completes the end-of-study assessments to 12 months after End of Treatment visit regardless of how many cycles a patient receives (Year 1=Day of First Treatment plus 12 months).
Year 2: Phone calls every other month (± 5 days) during Year 2 (Months 14 to 24 after End of Treatment visit).

* as clinically indicated

** only required if last pregnancy test was >72 hrs from C1D1 visit

*** optional for subsequent cycles for patients who have achieved a CR

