5.5 Follow-up Assessments

Patients will be contacted by telephone to record data on PBRC and/or platelet transfusions occurring within 56 days after the last dose of study drug. Patients will also be contacted by telephone to assess for date of death, date of stem cell transplant, date of relapse, or continued remission for 2 years:

- Year 1: Phone calls monthly (± 5 days) beginning the month after the patient completes the end-of-study assessments to 12 months after End of Treatment visit regardless of how many cycles a patient receives (Year 1=Day of First Treatment plus 12 months).
- Year 2: Phone calls every other month (± 5 days) during Year 2 (Months 14 to 24 after End of Treatment visit).

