6.2 Reasons for Withdrawal from Study Treatment

A patient may be permanently removed from study treatment for any of the following reasons:

- Failure to achieve a CR, CRi, CRh, PR, or clinical benefit. Patients not demonstrating evidence of CR, CRi, CRh, PR, or clinical benefit after the first cycle of treatment will be considered for removal from the study, although with permission of the Medical Monitor, treatment may continue if clinically indicated and provided there is no evidence of \geq Grade 3 toxicity considered at least possibly related to alvocidib.
- An excessive Grade 3-4 toxicity without a response to treatment or occurrence of any other adverse event, concurrent illness or laboratory abnormality which, in the opinion of the Principal Investigator, warrants the patient's permanent withdrawal
- Patient noncompliance, defined as refusal or inability to adhere to the study schedule;
- At the request of the patient, Principal Investigator, the Sponsor, or regulatory authority;
- Patient is lost to follow-up;
- Patient becomes pregnant while on study;
- Patient begins another treatment for their disease; or
- Patient death.

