6.3 Follow-up for Patients Withdrawn from Study Treatment

Patients withdrawn from study treatment with an ongoing adverse event must be followed clinically until the event is resolved, deemed stable or permanent by the PI, or the patient starts another treatment for their disease. A stable adverse event is defined as an event that is not expected to change in nature, severity or frequency. See [Section 8.4](#) through [Section 8.8](#) for reporting of adverse events. The pregnancy of any patient, or patient's partner, will be followed via monthly telephone calls until the birth of the child to term to record any birth defects/abnormalities.

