28- and 56-day TI will be summarized in 2x2 shift tables showing the percentages of patients who are transfusion independent at baseline according to review of medical charts versus the percentages of patients who achieve transfusion independence at any time during the study.

Effort will be made to collect transfusion information for 56 days following withdrawal from the study to properly classify a patient's post-treatment TI status. Patients not already classified as transfusion independent and who cannot be followed will be classified as 'status unknown' for the required time to establish TI.

Exploratory Endpoints

- To evaluate potential biomarkers including but not limited to MCL-1 dependence, genetic mutations, and other biomarkers associated with AML.
- Additional exploratory analyses may be performed if useful in the interpretation of the data.

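### Protocol 7.2 counts transfusion independence with no stop at the next leukemia therapy or transplant, so independence gained on another treatment can count as a study-drug success

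*SAP*

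**What the plan says.** **Scoring.** Protocol 7.2 (also the Synopsis and Section 3) plans shift tables of baseline status against the "percentages of patients who achieve transfusion independence at any time during the study". On data after treatment it adds: "Effort will be made to collect transfusion information for 56 days following withdrawal from the study". The stated purpose is to classify status after treatment. The only special handling is a status-unknown category for patients who are not yet independent and cannot be followed.

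**Collection.** The transfusion row in the schedules (Protocol Appendix A, SAP 18) reads "Recorded from 56 days prior to first study treatment dose, through 56 days after last dose of study treatment". The calls in Protocol 5.5 likewise ask about "transfusions occurring within 56 days after the last dose of study drug". These windows start from the last dose, whereas the one in 7.2 starts from withdrawal.

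**Next therapy.** Protocol 6.2 lists "Patient begins another treatment for their disease" as a reason to leave study treatment. Protocol 6.3 ends adverse-event follow-up when the event resolves or stabilizes, "or the patient starts another treatment for their disease"; 8.5 and 8.6 do the same. The calls in 5.5 are "to assess for date of death, date of stem cell transplant, date of relapse, or continued remission for 2 years", and no start date of other leukemia therapy is listed. After the first dose, Protocol 4.6.2 limits medication recording to drugs given for an adverse event.

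**SAP.** Section 3.2.2 keeps six TI endpoints. Section 11 lists best response and three response rates, with no TI derivation or table. Section 9.5.3 uses data from patients withdrawn from the study only up to withdrawal. Sections 1 and 16 say that the SAP supersedes the protocol's statistics, and Section 16 does not mention TI.

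**The concern.** TI is meant to describe what the study regimen achieves. Patients who stop early are likely to move to another therapy, and the protocol anticipates both that and transplant. A rule that accepts a qualifying run at any time and looks 56 days past treatment or withdrawal will, as written, accept a run that took place on the next treatment. The protocol already treats next therapy as a natural end point for adverse-event follow-up but sets no equivalent for TI. If the start date of that therapy is not collected, the affected days cannot be identified reliably at analysis. At stake is what six secondary rates mean, and for the patients enrolled, how a TI listing should be read.

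**Working it through.** The plan states no TI rate, so there is no figure to reproduce. The check is window arithmetic plus a comparison of the texts.

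**1. Direction.** Let A be the qualifying runs in the full window and B those completed before any next therapy or transplant. Every run in B is also in A. On a fixed denominator, successes under A are therefore at least as many as under B, and the rule as written can only match or exceed a rule with a cut-off.

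**2. Window from the last dose (Protocol 5.5, both schedules).** If next therapy starts s days after the last dose, a run of k days lies wholly on it only if s + k ≤ 56.
- k = 28: s ≤ 28.
- k = 56: s ≤ 0, so effectively never.

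Example: a one-cycle patient in either arm, with the last dose on nominal Day 15, has a window of Days 16 to 71 (71 − 16 + 1 = 56 days).
- Start on Day 30: 71 − 30 + 1 = 42 days on next therapy, and 42/56 = 75%. A 56-day run ending on Day 71 would include those 42 days, but the patient must also be transfusion-free from Day 16.
- Start on Day 44: 71 − 44 + 1 = 28 days, just enough for a 28-day run if the start day counts. If it does not, the limit is Day 43 (s = 28).

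The Cycle 1 marrow is due on Day 28 ± 3 (Protocol 5.2.6). A switch made soon after that result falls in the exposed range.

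**3. Window from withdrawal (Protocol 7.2).** If withdrawal coincides with the start of next therapy, all 56 following days are on it. Since 28 ≤ 56 and 56 ≤ 56, both run lengths can lie wholly on the next therapy.

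**4. Size per patient.** One patient counted only because of next therapy moves a rate by 100/n points.

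| n | Source | Points |
|---|---|---|
| 102 | selected arm, Stages 1 and 2 as planned | 1.0 |
| 26 | one Stage 1 arm as planned | 3.8 |
| 11 | all enrolled at closure | 9.1 |

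The n=11 row applies only if lead-in patients are included. SAP 6 and 8.1 put them in the overall column, while SAP 4 excludes them from efficacy analyses. With the 4 Stage 1 patients alone, one patient is 25 points.

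**5. Protocol 7.2 against SAP 9.5.3.**
- A patient leaves the study: 7.2 seeks and uses the next 56 days; 9.5.3 stops at withdrawal. The two conflict.
- A patient leaves study treatment but stays in follow-up: 9.5.3 does not apply, and nothing else stops the window. SAP 10.1 summarizes treatment and study discontinuation separately, so the distinction is the SAP's own.

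**The case against.** **The schedule row is not a scoring rule.** Correct. It says when transfusions are recorded. A reader might infer from it that TI is scored to 56 days after the last dose; the scoring language is in Protocol 7.2, which uses a different anchor. The point rests on 7.2.

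**The SAP supersedes the protocol and plans no TI table and no inference.** Also correct, and it limits the practical stake: the study closed with 11 patients and any output is descriptive. But SAP 3.2.2 retains the endpoints, SAP 9 lists all data, and nothing records that TI was dropped.

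**SAP 9.5.3 already cuts the data.** Only for withdrawal from the study, and applying it would contradict 7.2.

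**The days can be removed later.** In part. Transplant dates are collected, and starting other treatment is a listed reason for stopping. The case report forms may also hold a date; they are not among the documents. A reader might infer that affected days can never be removed. What the documents support is that the protocol text requires no start date for other anti-leukemic therapy.

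**Next therapy can also cause transfusions.** True, and it matters for a comparison with a world in which no next therapy was given. It does not alter the direction in step 1, which compares two ways of counting the same records.

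**Counting regardless of later therapy is a legitimate treatment-policy choice.** It is, if stated. Neither document states it, and it suits a rate meant to describe the study drug less well.

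**Conclusion.** The point holds: under Protocol 7.2 as written, independence gained on another therapy or after transplant can be counted as a study-drug success, and relative to a cut-off this can only raise the TI rates. With the last-dose window, complete misattribution is confined in practice to the three 28-day endpoints, and the 56-day endpoints overlap only partly. With the withdrawal window, all six are exposed.

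A reader might go further and infer that such runs will be credited to alvocidib, or that the rates are inflated by a known amount. The documents support neither. The SAP specifies no TI output, and no figure is given for how often or when patients start other therapy or how many would have their only qualifying run there. The supportable size is per patient: 1.0 point at n=102, 3.8 at n=26, 9.1 at n=11. The window arithmetic assumes nominal dosing days, and the direction assumes that the denominator is unchanged by the cut-off.

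**What to change.** 1. In Protocol 7.2 and SAP 3 and 11, use one anchor for the TI window, either last dose or withdrawal, and match the collection window to it.
2. Count TI only from transfusion-free runs completed before the start of any other anti-leukemic therapy or transplant. Say whether a patient whose window is cut short counts as not independent or as status unknown.
3. Reconcile Protocol 7.2 with SAP 9.5.3 on data after withdrawal.
4. Record the start date of subsequent anti-leukemic therapy at End of Treatment and on the existing follow-up call. The transplant date is already collected.
5. Apply the cut-off to any TI summary or listing for the enrolled patients, or state in SAP 16 that TI is not summarized.

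The cost is a few sentences and one extra date field, to be obtained for at most 11 patients. The downside is a possibly slightly lower TI rate.
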